**Table 5.5.1-2: PK and ADA Sampling Schedule for BMS-986148 Monotherapy QW Dosing Regimen**

Study Day of Sample Collection	Event	Time (Relative To Start of Infusion) Hour: Min	PK Sample (Serum and Plasma)	ADA Sample (Serum)
1	Predose	00:00	X	X
1	EOI	01:00	X	
1		04:00	X	
2		24:00	X	
4 a		72:00	X	
8	Predose	00:00	X	
8	EOI	01:00	X	
15	Predose	00:00	X	
15	EOI	01:00	X	
22		168:00	X	
Every 2 Cycles Starting at Cycle 5 (PK Only)				
1	Predose	00:00	X	
Every 4 Cycles Starting at Cycle 8 (PK and ADA)				
1	Predose	00:00	X	X
EOT			X	X
30-Day Follow-Up			X	
60-Day Follow-Up			X	X
Event Driven c			X	X

a EOI = Sample must be collected immediately following the end of the infusion. End of Infusion Serum will be collected for measuring total antibody, [REDACTED] and active ADC concentrations. Plasma will be collected for measuring [REDACTED] unconjugated tubulysin concentrations.

c In the event that labs are drawn and the subject is not dosed.

ADA: anti-drug antibody; ADC: antibody-drug conjugate; EOI: end of infusion; EOT: end of treatment; min: minimum; PK: pharmacokinetics; QW: every week.

**Table 5.5.1-3: PK and Anti-Drug Antibody Sampling Schedule for BMS-986148 Q3W Dosing Regimen in Combination with Nivolumab**

Study Day of Sample Collection	Event	Time (Relative to Start of Infusion) Hour:Min	BMS-986148 PK Sample (Serum and Plasma)	Nivolumab PK Sample (Serum)	BMS-986148 and Nivolumab ADA Samples (Serum)
Cycle 1					
1	Predose	00:00	X	X	X
1	EOI a	00:30		X	
1	EOI a	01:00	X		
1		04:00	X		
2 b		24:00	X	X	
4 ■		72:00	X	X	
8		168:00	X	X	
15		336:00	X	X	X
Cycle 2					
1	Predose	00:00	X	X	
1	EOI	00:30		X	
1	EOI	01:00	X		
Cycle 3					
1	Predose	00:00	X	X	X
1	EOI	00:30		X	
1	EOI	01:00	X		
Cycle 4					
1	Predose	00:00	X	X	X
1	EOI	00:30		X	
1	EOI	01:00	X		
1		04:00	X		
2 b		24:00	X	X	
4 ■		72:00	X	X	
8		168:00	X	X	
15		336:00	X	X	
Every 2 Cycles Starting at Cycle 5 (PK Only)					
1	Predose	00:00	X	X	

**Table 5.5.1-3: PK and Anti-Drug Antibody Sampling Schedule for BMS-986148 Q3W Dosing Regimen in Combination with Nivolumab**

Study Day of Sample Collection	Event	Time (Relative to Start of Infusion) Hour:Min	BMS-986148 PK Sample (Serum and Plasma)	Nivolumab PK Sample (Serum)	BMS-986148 and Nivolumab ADA Samples (Serum)
Every 5 Cycles Starting at Cycle 9 (PK and ADA)					
1	Predose	00:00	X	X	X
EOT			X	X	X
30-Day Follow-Up			X	X	X
60-Day Follow-Up			X	X	X
100-Day Follow-Up			X	X	X
Event Driven d			X	X	X

a EOI = Sample must be collected immediately following the end of the infusion. End of Infusion Serum will be collected for measuring total antibody, [REDACTED] and active ADC concentrations. Plasma will be collected for measuring [REDACTED] unconjugated tubulysin concentrations.

b ± 2 hours.

d In the event that labs are drawn and the subject is not dosed.

ADA: anti-drug antibody; ADC: antibody-drug conjugate; EOI: end of infusion; EOT: end of treatment; min: minimum; PK: pharmacokinetics; Q3W: every 3 weeks.

**Table 5.5.1-4: PK and Anti-Drug Antibody Sampling Schedule for BMS-986148 Q3W Dosing Regimen in Combination with Nivolumab During Retreatment**

Study Day of Sample Collection	Event	Time (Relative to Start of Infusion) Hour:Min	BMS-986148 PK Sample (Serum and Plasma)	Nivolumab PK Sample (Serum)	BMS-986148 and Nivolumab ADA Samples (Serum)
Cycle 1					
1	Predose	00:00	X	X	X
Cycle 3					
1	Predose	00:00	X	X	X
Cycle 4					
1	Predose	00:00	X	X	X

**Table 5.5.1-4: PK and Anti-Drug Antibody Sampling Schedule for BMS-986148 Q3W Dosing Regimen in Combination with Nivolumab During Retreatment**

Study Day of Sample Collection	Event	Time (Relative to Start of Infusion) Hour:Min	BMS-986148 PK Sample (Serum and Plasma)	Nivolumab PK Sample (Serum)	BMS-986148 and Nivolumab ADA Samples (Serum)
Every 5 Cycles Starting at Cycle 9					
1	Predose	00:00	X	X	X
EOT			X	X	X
30-Day Follow-Up			X	X	X
60-Day Follow-Up			X	X	X
100-Day Follow-Up			X	X	X
Event Driven a			X	X	X

a In the event that labs are drawn and the subject is not dosed.

ADA: anti-drug antibody; ADC: antibody-drug conjugate; EOI: end of infusion; EOT: end of treatment; min: minimum; PK: pharmacokinetics; Q3W: every 3 weeks.

### 5.5.2 Pharmacokinetic Sample Analyses

[figure not shown]
Serum samples for total antibody, [REDACTED] active ADC, and nivolumab concentrations and plasma samples for unconjugated tubulysin concentrations will be analyzed using a series of validated assays. [REDACTED]

### 5.5.3 Antibody-Drug Antibody Sample Analyses

[figure not shown]
ADA assessment utilizes a tiered approach to testing for ADA through detection, confirmation, and titer and domain specificity characterization as is applicable. All assay tiers are fully validated ligand binding assays.

### 5.5.4 Labeling and Shipping of Biological Samples

[figure not shown]
Detailed instructions for the PK blood collection, labeling, processing, storage, and shipping will be provided to the site in the procedure manual.

[figure not shown]

[figure not shown]

[figure not shown]

[figure not shown]

[figure not shown]

[figure not shown]

[figure not shown]
**5.8 Outcomes Research Assessments**

[figure not shown]
Not applicable.

**5.10 Results of Central Assessments**

Not applicable

## 6 ADVERSE EVENTS

An *AE* is defined as any new untoward medical occurrence or worsening of a preexisting medical condition in a clinical investigation subject administered study drug and that does not necessarily have a causal relationship with this treatment. An AE can therefore be any unfavorable and unintended sign (such as an abnormal laboratory finding), symptom, or disease temporally associated with the use of study drug, whether or not considered related to the study drug.

The causal relationship to study drug is determined by a physician and should be used to assess all AEs. The causal relationship can be 1 of the following:

- Related: There is a reasonable causal relationship between study drug administration and the AE.
- Not related: There is not a reasonable causal relationship between study drug administration and the AE.

The term “reasonable causal relationship” means there is evidence to suggest a causal relationship.

Adverse events can be spontaneously reported or elicited during open-ended questioning, examination, or evaluation of a subject. (In order to prevent reporting bias, subjects should not be questioned regarding the specific occurrence of 1 or more AEs.)

### 6.1 Serious Adverse Events

An *SAE* is any untoward medical occurrence that at any dose:

- Results in death
- Is life-threatening (defined as an event in which the subject was at risk of death at the time of the event; it does not refer to an event which hypothetically might have caused death if it were more severe)
- Requires inpatient hospitalization or causes prolongation of existing hospitalization (see **NOTE** below)
- Results in persistent or significant disability/incapacity

- Is a congenital anomaly/birth defect
- Is an important medical event (defined as a medical event(s) that may not be immediately life-threatening or result in death or hospitalization but, based upon appropriate medical and scientific judgment, may jeopardize the subject or may require intervention [eg, medical, surgical] to prevent 1 of the other serious outcomes listed in the definition above). Examples of such events include, but are not limited to, intensive treatment in an emergency room or at home for allergic bronchospasm; blood dyscrasias, or convulsions that do not result in hospitalization. p-DILI is also considered an important medical event. (See [Section 6.6](#) for the definition of p-DILI.)

Suspected transmission of an infectious agent (eg, pathogenic or nonpathogenic) via the study drug is an SAE.

Although pregnancy, overdose, cancer, and p-DILI are not always serious by regulatory definition, these events must be handled as SAEs (see Section 6.1.1 for reporting pregnancies).

Any component of a study endpoint that is considered related to study therapy (eg, death is an endpoint, if death occurred due to anaphylaxis, anaphylaxis must be reported) should be reported as SAE (see Section 6.1.1 for reporting details).

**NOTE:**

The following hospitalizations are not considered SAEs in BMS clinical studies:

- A visit to the emergency room or other hospital department < 24 hours that does not result in admission (unless considered an important medical or life-threatening event)
- Elective surgery, planned prior to signing consent
- Admissions as per protocol for a planned medical/surgical procedure
- Routine health assessment requiring admission for baseline/trending of health status (eg, routine colonoscopy)
- Medical/surgical admission other than to remedy ill health and planned prior to entry into the study. Appropriate documentation is required in these cases.
- Admission encountered for another life circumstance that carries no bearing on health status and requires no medical/surgical intervention (eg, lack of housing, economic inadequacy, caregiver respite, family circumstances, administrative reason).
- Admission for administration of anticancer therapy in the absence of any other SAEs (applies to oncology protocols)

### **6.1.1 Serious Adverse Event Collection and Reporting**

Sections 5.6.1 and 5.6.2 in the IB represent the Reference Safety Information to determine expectedness of serious AEs for expedited reporting. Following the subject's written consent to participate in the study, all SAEs, whether related or not related to study drug, must be collected, including those thought to be associated with protocol-specified procedures. All SAEs must be collected that occur during the screening period and within 60 days (or 100 days for combination

therapy) of discontinuation of dosing. If applicable, SAEs must be collected that relate to any later protocol-specified procedure (eg, a follow-up skin biopsy).

The investigator should report any SAE that occurs after these time periods and that is believed to be related to study drug or protocol-specified procedure.

An SAE report should be completed for any event where doubt exists regarding its seriousness.

If the investigator believes that an SAE is not related to study drug, but is potentially related to the conditions of the study (such as withdrawal of previous therapy or a complication of a study procedure), the relationship should be specified in the narrative section of the SAE Report Form.

SAEs, whether related or not related to study drug, and pregnancies must be reported to BMS (or designee) within 24 hours. SAEs must be recorded on the SAE Report Form; pregnancies on a Pregnancy Surveillance Form (electronic or paper forms). The preferred method for SAE data reporting collection is through the electronic case report form (eCRF). The paper SAE/pregnancy surveillance forms are only intended as a back-up option when the eCRF system is not functioning. In this case, the paper forms are to be transmitted via email or confirmed facsimile (fax) transmission to:

**SAE Email Address:** Refer to Contact Information list.

**SAE Facsimile Number:** Refer to Contact Information list.

For studies capturing SAEs through electronic data capture (EDC), electronic submission is the required method for reporting. The paper forms should be used and submitted immediately, only in the event the electronic system is unavailable for transmission. When paper forms are used, the original paper forms are to remain on site.

**SAE Telephone Contact** (required for SAE and pregnancy reporting): Refer to Contact Information list.

If only limited information is initially available, follow-up reports are required. (Note: Follow-up SAE reports should include the same investigator term(s) initially reported.)

If an ongoing SAE changes in its intensity or relationship to study drug or if new information becomes available, a follow-up SAE report should be sent within 24 hours to the BMS (or designee) using the same procedure used for transmitting the initial SAE report.

All SAEs should be followed to resolution or stabilization.

## **6.2 Nonserious Adverse Events**

A *non-SAE* is an AE not classified as serious.

### **6.2.1 Nonserious Adverse Event Collection and Reporting**

The collection of non-SAE information should begin at initiation of study drug. Non-SAE information should also be collected from the start of a placebo lead-in period or other observational period intended to establish a baseline status for the subjects.

Non-SAEs should be followed to resolution or stabilization, or reported as SAEs if they become serious (see [Section 6.1.1](#)). Follow-up is also required for non-SAEs that cause interruption or discontinuation of study drug and for those present at the end of study treatment as appropriate. All identified non-SAEs must be recorded and described on the non-SAE page of the CRF (paper or electronic).

Completion of supplemental CRFs may be requested for AEs and/or laboratory abnormalities that are reported/identified during the course of the study.

### **6.3 Laboratory Test Result Abnormalities**

The following laboratory test result abnormalities should be captured on the non-SAE CRF page or SAE Report Form (paper or electronic) as appropriate:

- Any laboratory test result that is clinically significant or meets the definition of an SAE
- Any laboratory test result abnormality that required the subject to have study drug discontinued or interrupted
- Any laboratory test result abnormality that required the subject to receive specific corrective therapy.

It is expected that wherever possible, the clinical rather than laboratory term would be used by the reporting investigator (eg, anemia versus low hemoglobin value).

### **6.4 Pregnancy**

If, following initiation of the investigational product, it is subsequently discovered that a study subject is pregnant or may have been pregnant at the time of study exposure, including during at least 5 half-lives after product administration, the investigator must immediately notify the BMS Medical Monitor/designee of this event and complete and forward a Pregnancy Surveillance Form to BMS Designee within 24 hours and in accordance with SAE reporting procedures described in [Section 6.1.1](#).

In most cases, the study drug will be permanently discontinued in an appropriate manner (eg, dose tapering if necessary for subject safety).

In the rare event that the benefit of continuing study drug is thought to outweigh the risk, after consultation with BMS, the pregnant subject may continue study drug after a thorough discussion of benefits and risk with the subject.

Protocol-required procedures for study discontinuation and follow-up must be performed on the subject unless contraindicated by pregnancy (eg, x-ray studies). Other appropriate pregnancy follow-up procedures should be considered if indicated.

Follow-up information regarding the course of the pregnancy, including perinatal and neonatal outcome and, where applicable, offspring information must be reported on the Pregnancy Surveillance Form.

Any pregnancy that occurs in a female partner of a male study participant should be reported to BMS. Information on this pregnancy will be collected on the Pregnancy Surveillance Form.

[figure not shown]
### 6.5 Overdose

All occurrences of overdose must be reported as SAEs (see Section 6.1.1 for reporting details).

### 6.6 Potential Drug-Induced Liver Injury

Wherever possible, timely confirmation of initial liver-related laboratory abnormalities should occur prior to the reporting of a p-DILI event. All occurrences of p-DILIs, meeting the defined criteria, must be reported as SAEs (see Section 6.1.1 for reporting details). The criteria for identifying p-DILI events depend on whether the subject's baseline liver biochemistry is normal or abnormal (see Figure 6.6-1).

**Figure 6.6-1: Algorithm for p-DILI Identification and Mandatory SAE Reporting in Subjects with (i) Normal Baseline Liver Biochemistry and (ii) Abnormal Baseline Liver Biochemistry**

ALT: alanine transaminase; AST: aspartate transaminase; SAE: serious adverse event; p-DILI: potential drug-induced liver injury; TB: total bilirubin; ULN: upper limit of normal.

The key responsibilities for investigators during p-DILI assessment include: (i) Early detection, medical evaluation (including the exclusion of other potential causes), and rapid laboratory confirmation of liver-related abnormalities, and (ii) BMS notification of p-DILI cases via SAE forms. Following the gathering and assessment of relevant clinical information BMS is responsible for: (iii) Timely evaluation and triaging of p-DILI cases, (iv) Expedited reporting of p-DILI cases, and (v) Expanded review of p-DILI cases including a detailed assessment of all available clinical information, investigations, and biochemical data.

Investigators are expected to monitor ongoing routine and ad hoc hepatic laboratory test results to rapidly determine whether a subject meets p-DILI criteria. They are expected to promptly notify BMS of all p-DILI cases. p-DILI cases may be identified by abnormal liver biochemistry values, whether or not they are accompanied by liver-related signs and/or symptoms. In both cases, expedited confirmation with repeat laboratory testing should occur within 3 business days using a Hepatic Laboratory Panel (ALT, AST, TB, and alkaline phosphatase). Any subject with an abnormal Hepatic Laboratory Panel that meets p-DILI criteria (see [Figure 6.6-1](#)) is a candidate for study drug discontinuation. Any confirmed p-DILI events must be reported (along with a description of the clinical findings) to BMS as an SAE within 24 hours of confirmation.

An extensive clinical history, examination, and appropriate investigations should be obtained to exclude cholestatic and other apparent causes that may explain the observed abnormalities in liver function and/or hepatic signs and symptoms. Other apparent causes include, nonexhaustively and by way of example only: infectious diseases (such as active hepatitis A, B, and C), congenital diseases (such as Gilbert's syndrome), neoplastic diseases (such as hepatocellular carcinoma), automimmune diseases (such as primary biliary cirrhosis), and the use of concomitant hepatotoxic medications (such as antibiotics, the oral contraceptive pill, and herbal medicines). All investigations to exclude potential causes of liver function abnormalities or hepatic signs and/or symptoms should be guided by relevant factors such as the subject's age, gender, clinical history, and signs and symptoms.

## **6.7 Other Safety Considerations**

Any significant worsening noted during interim or final PEs, ECG, x-ray filming, or any other potential safety assessment required or not required by protocol should also be recorded as a non-SAE or SAE, as appropriate, and reported accordingly.

## **7 DATA MONITORING COMMITTEE AND OTHER EXTERNAL COMMITTEES**

Not applicable

## **8 STATISTICAL CONSIDERATIONS**

### **8.1 Sample Size Determination**

Dose Escalation: In the monotherapy dose escalation part of the study, ie, both Parts 1A and 1B, a total of approximately 30 and 24 evaluable subjects are expected to be treated, respectively. The exact sample size per dose level cannot be precisely determined but depends on the observed DLT and will be guided by the mTPI design, with a target DLT rate of 27% (25% to 29%), based on Bayesian modeling and posterior inference. Between 2 and up to 13 DLT evaluable subjects may be enrolled to a given monotherapy cohort in Part 1A. Treating additional subjects beyond the 13 would be unlikely to alter the decision specified by the mTPI algorithm. In the combination dose escalation part (Part 3A), a total of approximately 12 evaluable subjects are expected to be treated across 2 dose levels, with the sample size per dose level guided by a mTPI design with target DLT rate of 29% (28% to 31%).

Cohort Expansion: During this part of the study, approximately up to 25 to 26 subjects in the population of interest [REDACTED] are expected to be treated in each tumor cohort at the MTD or alternate dose below the MTD (as determined from dose escalation), or other agreed dose level. This number per cohort is based on achieving a reasonable precision of the ORR and adequate control on the false negative rate (FNR) and false positive rate (FPR) (assuming a historic and target response rate as shown for monotherapy cohorts below):

In a cohort of 25 marker positive subjects, if 5 or 6 responses are observed (eg, for gastric or pancreatic cohorts), then the ORR 90% confidence intervals (CIs) are (8.2%, 37.5%) and (11%, 42%), respectively. If 7 responses are observed (eg, NSCLC and ovarian cohorts), then the 90% CI is (14%, 46.2%), and if 8 or 9 responses are observed (eg, mesothelioma cohort), then the 90% CIs for ORR are: (17%, 50.4%) and (20%, 54.4%), respectively. These calculations are based on the Clopper-Pearson method for exact CIs.

In addition, 25 subjects per cohort provide the following FNR and FPR under assumptions of expected true ORR. If the true ORR is 40% (eg, mesothelioma), then with 25 subjects in a cohort there is 97% and 93% chance of observing at least 6 or 7 responses, respectively, and there is 7% chance of observing 6 or fewer responses (FNR). If the true ORR for this tumor is only 20% (rather than 40%), then there is 22% and 11% chance respectively of observing at least 7 and at least 8 responses among 25 subjects (FPR).

Similarly if the true ORR is 20% (eg, gastric and pancreatic cohorts), then there is 97% and 90% probability of observing at least 2 or 3 responses respectively, among 25 subjects and 10% of observing 2 or fewer responses (FNR). If the true ORR for these tumors is 10% (rather than 20%) then there is 24% and 10% chance, respectively, of observing at least 4 and at least 5 responses (FPR).

If the true ORR is 30% (eg, NSCLC and ovarian cohorts), then there is 91% and 81% probability of observing at least 5 or 6 responses, respectively, in 25 subjects and 9% of observing 5 or fewer responses (FNR). If the true ORR for these tumors is 15% (rather than 30%) then there is 16% and 7% chance, respectively, of observing at least 6 and at least 7 responses (FPR).

The Simon 2-Stage design will be used in the monotherapy and nivolumab combination expansion cohorts, with a minimum of subjects treated initially as per the Stage 1 n of [Table 8.1-1](#) and [Table 8.1-2](#) below. Efficacy will be explored in both the [REDACTED] populations; there will be no adjustment for multiple comparisons. In each of monotherapy or combination cohorts after a minimum number of subjects (n for Stage 1) are treated, there will be an initial evaluation of efficacy independently in each cohort. If there is a lack of signal in either population, then treatment in that cohort may be stopped in that population; if there is an initial efficacy signal, subjects will continue to be treated in Stage 2 for the population in which there was a signal. [REDACTED]

The above results will inform potential early decisions and guide planning/operations or early termination after taking into consideration additional data, for example, duration of response

and/or SD and safety. The operational characteristics of these Simon 2-Stage designs are provided in the following tables.

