## 5 SAMPLE SIZE AND POWER

Dose Escalation: In the dose escalation part of the study, i.e., both Part 1A and 1B, the sample size per dose level cannot be precisely determined but depends on the observed DLTs and the decision rules of mTPI. Between 2 and up to 13 DLT evaluable subjects may be enrolled to a given cohort. Treating additional subjects beyond the 13 would be unlikely to alter the decision specified by the mTPI algorithm.

Cohort Expansion: During this part of the study approximately 25 subjects with high expression of mesothelin are expected to be treated in each tumor cohort at the maximally administered dose or at a dose near the MTD (as determined from dose escalation). This number is based on achieving a reasonable precision of the objective response rate (ORR) and adequate control on the false negative rate (FNR) and false positive rate (FPR) (assuming a historic and target response rate). In a cohort of 25 marker positive subjects if 5 or 6 responses are observed (e.g. for gastric or pancreatic cohorts) then the ORR 90% CI are (8.2%, 37.5%) and (11%, 42%), respectively. If 7 responses are observed (e.g. NSCLC cohort), then the 90% CI is (14%, 46.2%), and if 8 or 9 responses are observed (e.g. mesothelioma or ovarian cohorts), then the 90% CI for ORR are: (17%, 50.4%) and (20%, 54.4%), respectively. These calculations are based on the Clopper- Pearson method for exact confidence intervals.

In addition, 25 subjects per cohort provide the following FNR and FPR under assumptions of expected true ORR. If the true objective response rate (ORR) is 40% (e.g. mesothelioma and ovarian cohorts), then with 25 subjects in a cohort there is 97% and 93% chance of observing at least 6 or 7 responses, respectively, and there is 7% chance of observing 6 or fewer responses (false negative rate). If the true ORR for these tumors is only 20% (rather than 40%), then there is 22% and 11% chance respectively of observing at least 7 and at least 8 responses among 25 subjects (false positive rate).

Similarly if the true ORR is 20% (e.g. gastric and pancreatic cohorts), then there is 97% and 90% probability of observing at least 2 or 3 responses respectively, among 25 subjects and 10% of observing 2 or fewer responses (false negative rate). If the true ORR for these tumors is 10% (rather than 20%) then there is 24% and 10% chance respectively, of observing at least 4 and at least 5 responses (FPR).

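### Protocol Section 8.1: the text's false-negative rates disagree with the power in Table 8.1-1, and those for gastric/pancreatic and NSCLC/ovarian also disagree with the figures beside them

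*Protocol*

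**What the plan says.** Protocol Section 8.1 bases the cohort size on the precision of the ORR and on control of the FNR and FPR. It introduces the error rates with "25 subjects per cohort provide the following FNR and FPR under assumptions of expected true ORR" and then takes the tumor types in turn.

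- **Gastric and pancreatic, true ORR 20%:** 97% and 90% for at least 2 and at least 3 responses, then "among 25 subjects and 10% of observing 2 or fewer responses (FNR". At a true ORR of 10%: "24% and 10% chance, respectively, of observing at least 4 and at least 5 responses (FPR".
- **Mesothelioma, true ORR 40%:** 97% and 93% for at least 6 and at least 7, then "there is 7% chance of observing 6 or fewer responses (FNR". At a true ORR of 20%: 22% for at least 7 and 11% for at least 8.
- **NSCLC and ovarian, true ORR 30%:** 91% and 81% for at least 5 and at least 6, then an FNR of 9% for 5 or fewer. At a true ORR of 15%: 16% for at least 6 and 7% for at least 7.

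The same section says that a Simon 2-Stage design will be used. Table 8.1-1 gives alpha/power of 0.24/0.76 (gastric, pancreatic), 0.10/0.80 (mesothelioma) and 0.18/0.82 (NSCLC, ovarian). The Stage 1 boundaries are 0 of 15, 2 of 12 and 1 of 14. Neither document states a final cut-off.

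SAP Section 5 repeats the gastric/pancreatic rate ("of observing 2 or fewer responses (false negative rate", at 10%) and the 7% for mesothelioma. It groups ovarian with mesothelioma at 40%, gives no FNR or FPR for NSCLC, and describes no two-stage design.

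**The concern.** An FNR and an FPR describe a decision rule only if they share a cut-off. Moving the cut-off down lowers the FNR and raises the FPR, so quoting each at its more favourable cut-off describes a rule that does not exist. The gastric/pancreatic text does this. The NSCLC/ovarian text attaches a figure to the wrong event. All three stated FNRs are well below one minus the power in Table 8.1-1.

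These figures are offered as part of the reason for the cohort size. Someone relying on the prose would take the chance of missing an active drug in gastric or pancreatic cancer as 1 in 10, where the table implies about 1 in 4. With no final cut-off stated, that reader cannot tell which figure describes the decision to be made.

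**Working it through.** **Inputs.** ORR pairs, Stage 1/total n, boundaries and alpha/power come from Protocol Table 8.1-1. The cut-offs attached to each FNR and FPR come from the text of Section 8.1.

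**Formulas.** Single-stage, rule of at least r responses in n: FPR = P(X ≥ r | n, p0) and FNR = P(X ≤ r−1 | n, p1), exact binomial. Two-stage, with a stop at r1 or fewer of n1: P(success) = Σ over x1 > r1 of P(X1 = x1) · P(X2 ≥ r − x1), with n − n1 subjects in Stage 2. FNR = 1 − P(success) at p1.

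**Reproducing the plan's figures (single-stage, n = 25).**
- Gastric/pancreatic: P(X ≤ 2 | 0.20) = 0.8^25 + 25(0.2)(0.8^24) + 300(0.04)(0.8^23) = 0.0038 + 0.0236 + 0.0708 = 0.0982, stated as 10%. P(X ≥ 4 | 0.10) = 0.2364 and P(X ≥ 5 | 0.10) = 0.0980, stated as 24% and 10%. All reproduce.
- Mesothelioma: P(X ≤ 6 | 0.40) = 0.0736, P(X ≥ 7 | 0.20) = 0.2200, P(X ≥ 8 | 0.20) = 0.1091. All reproduce.
- NSCLC/ovarian: P(X ≥ 5 | 0.30) = 0.9095 and P(X ≥ 6 | 0.30) = 0.8065 reproduce. The 9% does not: P(X ≤ 5 | 0.30) = 1 − 0.8065 = 0.1935. The 9% is P(X ≤ 4) = 1 − 0.9095 = 0.0905. The sentence contradicts itself, since 81% for at least 6 leaves 19% for 5 or fewer.

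**FPR and FNR at a common cut-off.**

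| Cohort | Cut-off | Single-stage, n = 25: FPR / FNR | Two-stage: FPR / FNR |
|---|---|---|---|
| Gastric/pancreatic (15/25, r1 = 0) | ≥3 | 0.4629 / 0.0982 | 0.4485 / 0.1096 |
| | ≥4 | 0.2364 / 0.2340 | 0.2338 / 0.2382 |
| | ≥5 | 0.0980 / 0.4207 | 0.0977 / 0.4218 |
| Mesothelioma (12/25, r1 = 2) | ≥7 | 0.2200 / 0.0736 | 0.1852 / 0.1228 |
| | ≥8 | 0.1091 / 0.1536 | 0.0991 / 0.1849 |
| NSCLC/ovarian (14/26, r1 = 1) | ≥5 | 0.3179 / 0.0905 | 0.3237 / 0.0958 |
| | ≥6 | 0.1615 / 0.1935 | 0.1784 / 0.1746 |
| | ≥7 | 0.0695 / 0.3407 | 0.0821 / 0.3016 |

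For NSCLC/ovarian the two-stage column uses the table's total of 26.

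**Mesothelioma Stage 1 stop at ORR 40%.** P(X ≤ 2 | 12, 0.40) = 0.6^12 + 12(0.4)(0.6^11) + 66(0.16)(0.6^10) = 0.0022 + 0.0174 + 0.0639 = 0.0834 (unrounded sum). If the boundary is followed, no final cut-off can bring the FNR below 8.3%.

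**Against Table 8.1-1.** One minus power gives FNRs of 0.24, 0.20 and 0.18, against 10%, 7% and 9% in the text. The nearest two-stage rules are ≥4 of 25 (0.234 / power 0.762), ≥8 of 25 (0.099 / 0.815) and ≥6 of 26 (0.178 / 0.825).

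**The case against.** The strongest reply is that the text prints each cut-off beside its probability and says that the figures are for 25 subjects. The gastric/pancreatic and mesothelioma probabilities are correct for the events they name, and Table 8.1-1, in the same section, supplies the two-stage power. A careful reader can find the 0.76. The study also has no formal hypothesis test, and decisions weigh duration of response, stable disease and safety. This stands as a limit on the consequence. It does not rescue a 10% and a 24% offered together as one design's error rates, nor the NSCLC/ovarian 9%, which is wrong as printed.

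Three stronger readings are tempting, and the documents do not support them.

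- *That every cohort mixes cut-offs.* Mesothelioma's 7% FNR and 22% FPR share the rule of at least 7; only the additional 11% uses another. The NSCLC/ovarian wording pairs 5 or fewer with at least 6; its fault is the number.
- *That 7% is unattainable for mesothelioma.* The Stage 1 stop is permissive, follows a review of all available data, and enrollment may continue meanwhile. If it is never enforced, the single-stage 7.4% stands at a cut-off of 7.
- *That the final cut-offs are known.* They are inferred from the table. The mesothelioma inference is the least secure: power of 0.815 against a stated 0.80, and an early stopping probability of 0.45 where P(X ≤ 2 | 12, 0.20) = 0.558.

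**Conclusion.** The point holds, as a mismatch between text and table plus one wrong number. For gastric/pancreatic, the 10% FNR goes with an FPR of 46%, and the rule that fits Table 8.1-1 has an FNR of about 24%. This barely depends on the Stage 1 stop (23.4% without it, 23.8% with it). For NSCLC/ovarian, the 9% should be 19.3% for the event named, or about 17% for the two-stage rule of at least 6 of 26. For mesothelioma, the 7% is correct as a single-stage figure and is understated only if the boundary is followed: at least 8.3% at any cut-off, 12.3% at ≥7 and 18.5% at ≥8.

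The single-stage results need only the stated ORRs and n. The two-stage results assume that the boundary is applied and that the sample sizes are those of Table 8.1-1. A reader might infer that the cohorts are wrongly sized. That does not follow: the table's alpha/power pairs are close to achievable rules at the planned sizes. What fails is the prose account of them.

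**What to change.** In Protocol Section 8.1, replace the 10%, 9% and 7% FNRs with one final cut-off per tumor type, confirmed by the sponsor. Give the two-stage FPR and FNR of that cut-off, and say that they assume the Stage 1 boundary is followed. The cut-offs that best match Table 8.1-1, offered for confirmation, are:

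- gastric/pancreatic: ≥4 of 25, FPR/FNR 0.23/0.24;
- mesothelioma: ≥8 of 25, 0.10/0.18 (power 0.815 against the stated 0.80, so this row should be checked);
- NSCLC/ovarian: ≥6 of 26, 0.18/0.17.

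SAP Section 5 cannot simply take the same sentences. It should first be updated to the protocol's current two-stage design and ORR assumptions, including ovarian at 30% rather than 40%, and then carry the same figures.

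The cost is wording in the protocol, a somewhat larger update of one SAP section, and a sponsor decision on the cut-offs. No sample size, Stage 1 boundary or subject procedure changes. The stated FNRs become less favourable.
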